10. DATA COLLECTION PROCEDURES

All outcome measures were assessed by the same examiner at two time points: baseline (before initiation of treatment) and at the end of the 6-week intervention period.

JAMAR dynamometer and pinch meter measurements were performed according to the American Society of Hand Therapists (ASHT) standardized protocols. Three consecutive measurements were recorded for each strength test, with 30-second rest intervals between trials.

Home exercise adherence was monitored using exercise diaries. Patients recorded the date, number of sets and repetitions, and pain level for each session. Diaries were reviewed during weekly clinical sessions.

For the BFRE group, SpO₂ monitoring was performed throughout each session for safety.

11. STATISTICAL ANALYSIS PLAN

11.1 Software

All analyses were performed using IBM SPSS Statistics version 20.0 (IBM Corp., Armonk, NY, USA).

11.2 Descriptive Statistics

Continuous variables: mean +/- standard deviation (SD). Categorical variables: frequency (n) and percentage (%).

11.3 Normality Testing

The Shapiro-Wilk test was used to assess normality of data distribution, as recommended for small sample sizes ($n < 50$). Visual assessment was also performed using histograms and Q-Q plots.

11.4 Baseline Comparisons

One-way ANOVA was used to compare baseline demographic and clinical characteristics across the three groups. This was performed to verify successful randomization and ensure no significant pre-existing differences.

11.5 Primary Analysis — Time x Group Interaction

Mixed model ANOVA (repeated measures ANOVA with between-subjects factor) was used as the primary analytical method. This approach simultaneously evaluates:

- Within-subjects effect (time: pre vs. post-treatment)
- Between-subjects effect (group: BFRE vs. Eccentric vs. Orthosis)
- Time x Group interaction (differential treatment effects)

The time x group interaction was the primary focus, testing whether one treatment method produced a statistically significantly different rate or magnitude of improvement compared to the others.

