7. OUTCOME MEASURES

7.1 Primary Outcome

Visual Analog Scale (VAS): A 10-cm horizontal line where 0 = no pain and 10 = worst imaginable pain. Patients marked their current pain level. Assessed at baseline and 6 weeks.

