8. SAMPLE SIZE CALCULATION

Sample size was calculated using G*Power software (version 3.1.9.4, Faul et al., 2007).

Parameters: Effect size = 1.8 (based on previously reported pain reduction rates in lateral epicondylitis exercise studies); Type I error rate $\alpha = 0.05$; Statistical power = 95% ($1 - \beta = 0.95$).

Result: Minimum 9 participants per group, total N = 27.

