11.8 Significance Level

The significance level was set at $p < 0.05$ for all analyses (two-tailed).

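### With one baseline and one 6-week value, the primary time-by-group test is a change-score ANOVA; a baseline-adjusted ANCOVA, labelled post hoc, should be reported beside it

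*Combined protocol and SAP*

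**What the plan says.** Section 7.1 defines the primary outcome as VAS pain on a 0-10 cm line: "Patients marked their current pain level. Assessed at baseline and 6 weeks". Section 10 confirms the schedule for every outcome: "All outcome measures were assessed by the same examiner at two time points".

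Section 11.5 names the model: "Mixed model ANOVA (repeated measures ANOVA with between-subjects factor) was used as the primary analytical method". Of its three effects, "The time x group interaction was the primary focus".

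Baseline enters the plan as the first level of the time factor, as the denominator of the percentage change in section 11.9, and in the one-way ANOVAs of section 11.4, of which the plan says: "This was performed to verify successful randomization and ensure no significant pre-existing differences". No model in section 11 uses a baseline value as a covariate.

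Section 8 gives 9 patients per group and 27 in total. Section 11.10 reports complete data, and section 13 places the statistical analyses in December 2024.

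**The concern.** A change score subtracts the whole baseline value, which amounts to assuming that a patient who starts 1 cm higher will finish 1 cm higher. If the true slope is smaller, a group that starts high by chance shows a larger fall merely through regression to the mean, and the group comparison absorbs it. With 9 per group such chance differences are ordinary.

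Section 11.4 treats a non-significant baseline test as assurance, but a test with so few patients misses large imbalances, and its result does not change how the primary comparison is made.

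Two things are at stake: precision in a trial that lists limited power among its own limitations (section 14), and how far the primary p-value can be trusted if baseline VAS happened to differ between the groups.

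**Working it through.** **Inputs from the documents.** Three groups of 9; two time points; two-sided 0.05; no missing data. Pre-post correlation rho and VAS SDs: not given. Assumed here: normal data, rho from 0.3 to 0.9, and s = SDpost/SDpre equal to 1, with 0.7 and 1.3 as sensitivity values.

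**The plan's own figure.** Section 8 gives: "Effect size = 1.8 (based on previously reported pain reduction rates in lateral epicondylitis exercise studies", with 95% power. Read as a standardised difference between two groups, n = 2(1.960 + 1.645)²/1.8² = 25.99/3.24 = 8.02, rounded up to 9 per group. The stated figure reproduces under this normal approximation (noncentral-t power at 9 per group is 0.9475). It contains no rho, and the plan does not say whether 1.8 is in raw or change-score SD units, so it does not settle the present question.

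**Step 1: equivalence.** On a test data set of 3 x 9, the interaction F and the one-way ANOVA F on change were both 1.17846 on 2 and 24 df. With two time points the identity is exact.

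**Step 2: variance of a group contrast**, in units of SDpre²:
- change score: proportional to 1 + s² − 2·rho·s
- ANCOVA: proportional to s²(1 − rho²)
- ratio at s = 1: (1 − rho²)/[2(1 − rho)] = (1 + rho)/2
- factor for estimating the slope from 24 error df: 1 + 1/22 = 1.045

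| rho (s = 1) | (1 + rho)/2 | with factor | 27/ratio, patients |
|---|---|---|---|
| 0.3 | 0.65 | 0.68 | 40 |
| 0.5 | 0.75 | 0.78 | 34 |
| 0.7 | 0.85 | 0.89 | 30 |
| 0.8 | 0.90 | 0.94 | 29 |
| 0.9 | 0.95 | 0.99 | 27 |

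The last column is the number of patients a change-score analysis would need for the same precision. Simulated variance ratios were 0.67, 0.79, 0.89, 0.95 and 0.99.

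**Step 3: unequal SDs.** At s = 1.3 and rho 0.5: 1.69 × 0.75/(2.69 − 1.30) = 0.912, times 1.045 = 0.95. At rho 0.7 and 0.8 the result is 1.04, a slight loss. At s = 0.7 it is 0.42 to 0.51 across rho 0.3 to 0.9, a larger gain than with equal SDs.

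**Step 4: power and agreement (simulation, s = 1).** For true means 0, 0.75 and 1.5 SD, power goes from about 0.62 (change score) to 0.79 (ANCOVA) at rho 0.3, from 0.77 to 0.86 at 0.5, and from 0.94 to 0.96 at 0.7. At rho 0.8 it is 0.991 against 0.994. In a second scenario, with the groups 0, 0.5 and 1.0 SD apart, both methods recovered the true contrast on average, but their overall tests disagreed on significance in 22%, 20%, 13%, 7% and 1% of trials at rho 0.3, 0.5, 0.7, 0.8 and 0.9.

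**Step 5: chance imbalance.** Each baseline mean has a standard error of 1/√9 = 1/3 SD. The expected range of three such means is 0.56 SD, and the range exceeds 0.5 SD in 54% of trials. Over all trials both tests have 5% type I error. In the roughly 20% of trials where the range exceeds 0.8 SD, change-score type I error is about 12%, 10% and 8% at rho 0.3, 0.5 and 0.7, against about 5% for ANCOVA.

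**Step 6: can section 11.4 detect this?** The critical F on 2 and 24 df is 3.40. For three equally spaced means with range R in SD units, F is about 9R²/4, so significance needs R = √(3.40 × 4/9) = 1.23 SD. With two means equal and one apart, F is about 3R² and R must reach √(3.40/3) = 1.06 SD. Imbalances of 0.8 to 1 SD would therefore typically pass.

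**The case against.** The strongest reply is that the planned test is legitimate. Under randomisation it is unbiased and holds 5%, so the choice is one of efficiency, and the size of the gain rests on a correlation and SDs that the documents do not report. That stands. It is why the gain is given as a range that includes nil and a small loss.

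The second reply concerns timing. Recruitment ended in October 2024 and the analyses are dated December 2024. Changing the primary model now would be a choice made after the data were seen, with a real chance of changing the significance result (Step 4). That also stands and governs the fix.

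A reader might infer several stronger points that the documents do not support:
- *ANCOVA gives the same answer.* Only the expected treatment difference is the same; estimates and p-values in one trial can differ.
- *ANCOVA is clearly more precise here.* That would need rho and s, which are not given.
- *ANCOVA removes chance imbalance.* It corrects the contrast for the linear effect of baseline VAS only; imbalance in other characteristics remains.
- *Any rho below 1 means over-correction.* The condition is rho × s below 1.
- *Section 11.4 applies ANOVA to categorical variables.* The section does not list the characteristics tested, and section 11.2 treats categorical variables separately, so at most the wording is unclear.

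**Conclusion.** The point holds as a recommended improvement, not as an error that invalidates the primary result. The primary test is exactly a change-score ANOVA, baseline VAS is collected on everyone but is not a covariate in any model, and the baseline tests in section 11.4 neither ensure balance nor correct for its absence.

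With equal SDs, adjustment would cut the variance of a group contrast by about 32%, 22% and 11% at rho 0.3, 0.5 and 0.7, and by little or nothing from 0.8. The precision gain therefore depends on undocumented quantities, which the investigators can read from their own data. The protection when baseline VAS differs by chance applies whenever the true slope is below 1. It matters most at low rho and shrinks as the slope approaches 1.

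**What to change.** 1. Add to section 11.5 an ANCOVA of 6-week VAS on group (three levels) and baseline VAS, with the 2-df group test on 23 error df, adjusted pairwise differences and 95% confidence intervals.
2. Do the same for grip strength, pinch strength and DASH, each with its own baseline. The figures above assume a generic rho and s; no separate calculation was made for these outcomes.
3. Label it a post hoc baseline-adjusted analysis and show it beside the planned mixed ANOVA, which stays as the stated primary test. ANCOVA would be the primary model only if it had been specified before the data were seen.
4. Report the observed pre-post correlation and the SDs at both visits, so that readers can see which row of the table applies.
5. In section 11.4, replace the baseline p-values with descriptive summaries by group.

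The cost is one error degree of freedom (24 to 23), one rerun in the same software on data already complete, and a second result that may disagree with the planned test and would then have to be discussed openly.

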11.6 Within-Group Comparisons

Paired t-tests were used to compare pre- and post-treatment values within each group. This analysis assessed the statistical significance of change for each intervention separately.

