3. STUDY OBJECTIVES AND HYPOTHESES

Primary Objective: To compare the effectiveness of BFRE, eccentric exercise, and orthosis use on pain reduction in patients with lateral epicondylitis.

Secondary Objectives: To compare the effects of the three interventions on hand grip strength, pinch strength, and upper extremity functional disability.

Hypotheses:

H0: There is no difference between BFRE, eccentric exercise, and orthosis groups in terms of functional level, pain, and grip strength.

H1: BFRE has a significant effect on functional level, pain, gross and fine grip strength in patients with lateral epicondylitis.

H2: Eccentric exercise has a significant effect on functional level, pain, gross and fine grip strength compared with BFRE in patients with lateral epicondylitis.

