11.9 Effect Size and Percentage Change

Percentage change from baseline was calculated for each outcome measure within each group to provide clinically interpretable effect magnitudes: $[(\text{Post} - \text{Pre}) / \text{Pre}] \times 100$.

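### H1 names no comparator and no test is assigned to decide it, so the BFRE arm's own pre-post change could be read as proof that BFRE works

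*Combined protocol and SAP*

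**What the plan says.** Section 3 of the combined protocol and SAP lists three hypotheses. The null is between-group: "There is no difference between BFRE, eccentric exercise, and orthosis groups in terms of functional level, pain, and grip strength". H2 names a comparator: "Eccentric exercise has a significant effect on functional level, pain, gross and fine grip strength compared with BFRE". H1 does not: "H1: BFRE has a significant effect on functional level, pain, gross and fine grip strength in patients with lateral epicondylitis".

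Section 11.5 makes a mixed ANOVA the primary method and says that "The time x group interaction was the primary focus". Section 11.7 adds pairwise comparisons after a significant ANOVA, without naming which pairs bear on which hypothesis.

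Section 11.6 then plans a separate test in each arm: "Paired t-tests were used to compare pre- and post-treatment values within each group". Its stated purpose is: "This analysis assessed the statistical significance of change for each intervention separately". Section 11.8 sets two-tailed p < 0.05 for all analyses, which includes these tests. Section 11.9 adds a second within-arm summary: "Percentage change from baseline was calculated for each outcome measure within each group to provide clinically interpretable effect magnitudes".

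All three arms receive a wrist orthosis and stretching (sections 1 and 6.1 to 6.3), and section 12 confirms that there is no untreated arm.

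**The concern.** A paired t-test in the BFRE arm asks whether patients in that arm changed over six weeks. It does not ask whether BFRE caused the change. The pre-post difference combines any BFRE effect with the orthosis and stretching given in every arm, natural recovery, and regression to the mean in patients who enter with symptoms. Only a contrast between randomised arms removes what the arms share.

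H1 has no comparator, and the plan assigns no test to it. The paired t-test is the only listed analysis of the BFRE arm on its own, so it is the one that fits H1 most literally. The time effect in the mixed ANOVA does not help, because it pools all arms and has the same weakness.

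Two errors become possible in the report. H1 may be declared confirmed although BFRE adds nothing. Arms may also be ranked because one reaches p < 0.05 and another does not, which is not a test of the difference between them.

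**Working it through.** **Inputs from the documents.** 9 patients per arm, three arms, no dropouts (sections 8 and 11.10); two-sided 0.05 for every analysis (section 11.8); one pre and one post value per outcome (section 10).

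**Assumptions.** The documents give no SD, pre-post correlation or expected change. I assume normal data, a pre-post correlation ρ of 0.5, and the same true improvement δ (in baseline SD units) in all three arms, so that BFRE adds nothing. I show δ from 0.5 to 1.5.

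**The plan's own figure.** Reading the section 8 effect size of 1.8 as a two-group standardised difference, n per group = 2(1.960 + 1.645)² / 1.8² = 8.02, rounded up to 9. This matches the stated 9 per group. It confirms n = 9 for the calculation below and says nothing about which test decides H1.

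**Step 1: scale of the change.** SD of change = SD × √(2(1 − ρ)) = SD × √(2 × 0.5) = SD. The standardised change d_z therefore equals δ.

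**Step 2: chance that the BFRE paired test is significant.** The statistic is noncentral t with 8 degrees of freedom and noncentrality d_z × √9 = 3d_z. The critical value is 2.306. Call the resulting probability p.

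**Step 3: chance that some but not all arms are significant.** The arms are independent, so this is 1 − p³ − (1 − p)³. At δ = 0.8, for example, 1 − 0.559³ − 0.441³ = 1 − 0.175 − 0.086 = 0.739.

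**Step 4: chance that BFRE is significant and orthosis is not.** This is p(1 − p).

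**Step 5: the interaction test.** With two time points it is equivalent to a one-way ANOVA on change scores. It was simulated under the same equal improvement.

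| Common improvement (SD) | BFRE paired test p < 0.05 | Some but not all arms significant | BFRE significant, orthosis not | Interaction p < 0.05 | BFRE paired test significant, interaction not |
|---|---|---|---|---|---|
| 0.5 | 26% | 58% | 19% | about 5% | 24% |
| 0.8 | 56% | 74% | 25% | about 5% | 53% |
| 1.0 | 75% | 57% | 19% | about 5% | 71% |
| 1.5 | 97.5% | 7% | 2% | about 5% | 93% |

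The two hazards do not peak together. A false confirmation of H1 becomes more likely as the common improvement grows. A spurious ranking is most likely at a moderate improvement (74% at 0.8 SD) and nearly vanishes at 1.5 SD, where almost every arm is significant.

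**What the between-group test can do.** An unadjusted two-sided BFRE-versus-orthosis comparison of change at 9 per arm has power of about 95% for a difference of 1.8 SD of change, 85% for 1.5, 51% for 1.0 and 36% for 0.8. If the true difference is around 1 SD or less, a non-significant between-group result alongside significant paired tests is a realistic outcome.

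**The case against.** The strongest reply is that the plan is already comparative where it counts. The primary objective is to compare the three treatments, section 11.5 puts the interaction first, and section 11.7 supplies pairwise tests after a significant ANOVA. H1 is listed as an alternative to a three-group null, so it can be read as a loosely worded between-group hypothesis. Section 11.6 claims only to assess change. On this view harm arises only if someone sets the primary analysis aside.

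Much of this stands. A reader might infer that the plan makes the paired t-tests the decision rule for H1, or that following it leads to arms being ranked on within-arm significance. The documents do not support either reading: no section assigns H1 to section 11.6, and none ranks arms that way. The link is an inference from H1's wording and the list of analyses. The primary test is not at fault.

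Two further readings should also be resisted. H2 might look one-directional and so at odds with two-tailed testing, but it names a comparator without claiming superiority, and a two-tailed test would not inflate false positives in any case. Nor is the BFRE-versus-orthosis contrast wholly absent: neither H1 nor H2 states it, but the null covers all three groups, and the pairwise comparisons would include that pair after a significant ANOVA.

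The reply does not close the gap. When the interaction is not significant, section 11.7 yields no pairwise test. The paired tests are then the only arm-specific p-values left, at full p < 0.05 status, beside a hypothesis that they appear to answer. Section 14 itself concedes that 9 per group limits power.

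**Conclusion.** The concern holds as a fault in the wording of H1 and in the unstated role of section 11.6, not as a fault in the primary analysis. H1 can be accepted as worded from evidence that does not use the randomisation. If all arms improve equally, that evidence appears in about a quarter of trials at 0.5 SD and in nearly all at 1.5 SD, against about 5% for the interaction test.

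These rates rest on an assumed common improvement and a correlation of 0.5, neither of which the documents give. That all arms improve is an expectation from shared treatment and natural course, not a stated figure. The qualitative conclusion does not depend on them: any real improvement common to all arms raises the paired test's rejection rate above 5% without any BFRE effect.

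Severity: should be fixed. The primary inference is already between-group, but the ambiguity concerns the headline claim for the experimental treatment.

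**What to change.** - State that H1 is judged on the two-sided between-group difference in change, BFRE plus orthosis and stretching versus orthosis and stretching, with VAS as the primary outcome and grip strength, pinch strength and DASH as secondary.
- State that H2 is judged on the two-sided eccentric-versus-BFRE difference in change.
- In sections 11.6 and 11.9, report within-arm change as a mean with 95% CI, labelled descriptive. State that no effectiveness claim and no ranking of arms rests on paired t-test p-values or on within-arm percentage change.
- Disclose this as a post hoc clarification. Section 13 places recruitment and interventions up to October 2024 and analysis in December 2024, and sections 11.10 and 11.11 already describe the collected data. It should not be presented as a prespecified hypothesis.

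The cost is wording in sections 3, 11.6 and 11.9 and in the report. It removes 12 p-values as evidence (3 arms × 4 outcomes) and needs no new data. The remaining price is candour about precision: the between-group intervals at 9 per arm will be wide, and the report should show them.

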11.7 Post-Hoc Analyses

When significant differences were detected by ANOVA, post-hoc pairwise comparisons were performed to identify the source of the difference.

11.8 Significance Level

The significance level was set at $p < 0.05$ for all analyses (two-tailed).

11.9 Effect Size and Percentage Change

Percentage change from baseline was calculated for each outcome measure within each group to provide clinically interpretable effect magnitudes: $[(\text{Post} - \text{Pre}) / \text{Pre}] \times 100$.

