5. STUDY POPULATION

5.1 Inclusion Criteria

1. Clinical diagnosis of lateral epicondylitis confirmed by an orthopedic surgeon
2. Age 18 years or older
3. Unilateral lateral epicondylitis
4. Signed written informed consent form

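### Between-group differences are tested but never estimated with an interval, and within-group percentage change is the only effect magnitude the plan names

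*Combined protocol and SAP*

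**What the plan says.** The primary objective (section 3) is comparative: "To compare the effectiveness of BFRE, eccentric exercise, and orthosis use on pain reduction in patients with lateral epicondylitis".

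The SAP addresses it through tests:

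- **11.5** makes a mixed ANOVA the primary method: "The time x group interaction was the primary focus, testing whether one treatment method produced a statistically significantly different rate or magnitude of improvement" compared with the other arms.
- **11.7** adds pairwise work on a condition: "When significant differences were detected by ANOVA, post-hoc pairwise comparisons were performed to identify the source of the difference". It names no estimate, interval or multiplicity method.
- **11.6** is within-arm: "Paired t-tests were used to compare pre- and post-treatment values within each group".
- **11.2** reports continuous variables as mean and SD.

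Section 11.9 is the only one on effect size for the results: "Percentage change from baseline was calculated for each outcome measure within each group to provide clinically interpretable effect magnitudes". Its formula is post minus pre, divided by pre, times 100. The other effect size in the document, 1.8 in section 8, is a sample-size input.

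No section mentions a confidence interval, an estimated difference between arms, or a standardised between-group effect.

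**The concern.** The quantity labelled as the effect does not answer the trial's question, for three reasons.

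1. **It is not comparative.** All three arms receive the orthosis and stretching (6.1 to 6.3, 6.5), and section 12 confirms that there is no untreated group. Change within an arm therefore contains natural recovery and the shared treatment as well as any effect of the exercise. Only a contrast between arms separates these. H1 in section 3 gives BFRE a significant effect without naming a comparator, so a large within-arm percentage could be taken as support for it.
2. **It depends on baseline.** Arms with equal absolute benefit show different percentages if their baselines differ, and with 9 per arm chance differences in baseline are plausible.
3. **It is not fully defined.** The mean of individual percentages and the percentage change of the means are different numbers, and 11.9 does not choose between them.

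If the interaction is not significant, the plan yields a p-value, means with SDs, paired tests and three sets of percentages. Nothing shows how large a difference between arms remains compatible with the data, so the result could be read as equal effectiveness.

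**Working it through.** **Inputs.** 9 per arm, total 27 (section 8); two-sided 5% level (11.8); VAS from 0 to 10 cm, described as "A 10-cm horizontal line where 0 = no pain and 10 = worst imaginable pain" (7.1); all 27 patients complete (11.10). The documents give no SD for VAS or for its change.

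**The plan's own figure.** The plan states no precision. The only related figure is the sample size. A two-group normal approximation with a standardised difference of 1.8 and 95% power gives 2 × (1.960 + 1.645)² / 1.8² = 8.02, rounded up to 9 per group. The stated figure reproduces on that basis and is used below only as the source of n = 9.

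**Baseline dependence.** A fall of 2 cm, as -2 / pre × 100:

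| Baseline VAS (cm) | Percentage change |
|---|---|
| 8 | -25% |
| 6 | -33% |
| 4 | -50% |
| 2 | -100% |

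**Per patient or from means.** Take two patients, one going from 2 to 1 and one from 8 to 7.

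- Mean of individual percentages: (-50 - 12.5) / 2 = -31.25%.
- From means: 5 to 4, which is -20%.

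**Precision of a pairwise difference in mean change.** With two visits, the time-by-group interaction is the comparison of mean change across arms, so the matching variance is the pooled variance of change, on 27 - 3 = 24 df. The half-width is t × SD × √(2/9), with √(2/9) = 0.4714.

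- 95%: t(0.975, 24) = 2.064, giving 0.973 SD.
- Bonferroni for three pairs: t(1 - 0.05/6, 24) = 2.574, giving 1.213 SD.

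In centimetres, over an assumed range for the SD of change:

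| Assumed SD of change (cm) | 95% half-width (cm) | Bonferroni half-width (cm) |
|---|---|---|
| 1.5 | ±1.46 | ±1.82 |
| 2.0 | ±1.95 | ±2.43 |
| 2.5 | ±2.43 | ±3.03 |

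Even an observed difference of exactly zero would leave differences of this size open in either direction. A baseline-adjusted model has 23 df and a multiplier of 0.975, applied to its residual SD.

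**The case against.** The strongest reply is that the plan's inference is between-group. The interaction is the primary focus, pairwise comparisons follow if the ANOVA is significant, and 11.9 is a descriptive supplement on which no test relies. Means and SDs in original units let a reader form absolute differences. Section 14 already admits that 9 per group limits power.

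Much of this stands, and it rules out several stronger readings that a reader might infer:

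- **That the plan has no between-group analysis.** Sections 11.5 and 11.7 contradict this. What is missing is an estimate with an interval.
- **That the percentages will be compared across arms.** Section 11.9 does not say so. It does call them effect magnitudes and offers no other.
- **That the trial will claim equal effectiveness.** No section says this, and the limitation on power points the other way. The risk is one of interpretation.
- **That the formula breaks down at a zero baseline.** Entry rests on "Clinical diagnosis of lateral epicondylitis confirmed by an orthopedic surgeon", age, unilateral disease and consent, with no minimum VAS or DASH, so low individual scores are permitted. The problem arises mainly if percentages are computed per patient. A zero group mean for pain among diagnosed patients is very unlikely.

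The reply does not remove the gap. Admitting low power does not tell the reader how wide the uncertainty is. Visit-level means and SDs give the point difference in change, but its interval also needs the correlation between visits, which the plan does not report.

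**Conclusion.** The point holds as a gap in estimation and reporting, and should be corrected. The primary test is not invalidated by it. The plan tests between-group differences without estimating them, and the one effect magnitude it names is non-comparative, baseline-dependent and incompletely defined.

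The size is material. A pairwise 95% interval extends 0.97 SD of change either side (1.21 SD with Bonferroni), about ±1.5 to 2.4 cm (Bonferroni 1.8 to 3.0 cm) on a 10 cm scale. The multipliers rest on 9 analysed patients per arm and a common variance of change. The centimetre figures rest also on the assumed SD of 1.5 to 2.5 cm and are illustrative; the trial's own data can replace them.

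**What to change.** Rewrite 11.9 along these lines:

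*For each outcome, the effect measure is the difference between groups in mean change from baseline to 6 weeks, in original units (cm, kg, DASH points), for each pair of groups, with a 95% CI and [named multiplicity method]. It is reported whether or not the ANOVA is significant. Percentage change is descriptive only, and its method of calculation (per patient or from group means) is stated. A non-significant test is not evidence of equal effectiveness.*

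The difference in mean change matches the interaction in 11.5, so test and estimate come from one model. The baseline-adjusted difference at 6 weeks is an acceptable alternative only if 11.5 is changed to the same model. The multiplicity method should be the same as that used in 11.7, which also needs to name one.

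The cost is small: no new data, since 11.10 reports all 27 patients complete, a short re-analysis, and one extra table. Section 13 places the statistical analyses in December 2024, so the estimates must be labelled as added after the original analysis.
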